## Feasibility of Recruitment and Retention

The investigative team has a track record of high enrollment in industry-sponsored and extramurally funded clinical trials in patients undergoing cardiac surgery. The original study end point of 280 patients over a 56-month enrollment period required approximately 5 to be enrolled each month. The study endpoint of 350 patients in the second phase of the study requires enrollment of approximately 8 patients/month, a rate that we feel is attainable based on our success in the first phase of the study. The volume of surgical procedures performed at Northwestern Memorial Hospital (Table 6) will allow for the study to be completed in the planned timeframe. Procedures for retention of patients in the study will include visits by the nurse coordinators to the patients during hospitalization to reinforce the importance of the study. The patients will be contacted by phone before the 4-to-6-week postoperative visit to confirm their testing session.

**Table 6: Number of Cardiac Procedures at Northwestern Memorial Hospital**

Type of procedure	2014	2015
Coronary artery bypass graft surgery	177	144
Mitral valve procedure	134	119
Aortic valve procedure	286	264
Multiple procedures	198	186
Other CV (VAD, ECMO, Heart transplant)	88	124

This surgical volume and the track record of the PI and other investigators in enrolling patients in clinical trials involving cardiac surgical patients ensures that an adequate number of patients will be enrolled to complete this trial in the funding period.

## Statistical Analysis Plan

Tabular and graphical methods of data exploration will be used to evaluate variable distributions over the perioperative time period. When conducting modeling, we will determine the influence of the outliers on model fit. If the influence is high, we will consider excluding the outlier/s. We will explore the extent to which CBF autoregulation changes over the perioperative period. Univariate distributions for all study variables will be evaluated. We will explore potential confounders as variables strongly predictive of the outcomes (a priori and in the data) and differentially distributed between the study arms. Results of these analyses will be used to refine the analyses and guide model building and selection.

The cognitive outcome will be assessed as change from baseline in a composite cognitive Z score 4 to 6 weeks after surgery. The Z score will be calculated for individual tests at each testing time point with the mean and SD of baseline tests of all patients. Timed tests will be multiplied by '-1' so that higher scores represent better performance. Individual Z scores will be combined into an average Z-score, calculated from the average of the non-missing individual test Z-scores. These will then be renormalized using the mean and standard deviation at baseline. A difference between pre- and post-test  $> 0.3$  is considered cognitive decline.

Early stopping rules: N/A

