## **Detection of Brain Injury**

Brain injury after cardiac surgery has a range of clinical manifestations, including clinical stroke (detected in ~2%–5% of patients) and cognitive decline (reported in 18%–40% of patients, depending on statistical criteria and timing of testing). Cognitive testing has methodologic limitations that lower its sensitivity and specificity for detecting neurologic injury (as opposed to its use for studying the effects of surgery on cognition), including difficulty with distinguishing the confounding effects of preexisting cerebral vascular disease. Moreover, preexisting brain infarction is associated with cognitive impairment, regardless of surgery, thus lowering the likelihood of being able to diagnose further cognitive decrement from new injury or “basement effect.” Nonetheless, our data indicate that cardiac surgery results in changes in cognition indicative of brain injury. Cognitive decline, though, appears to be a transient phenomenon, with most individuals returning to near baseline by 3–6 months after surgery. More controversial is the relationship between perioperative cognitive decline and long-term cognitive decline. Data from our colleagues suggest that the rate of long-term cognitive decline is not different for patients undergoing CABG surgery than it is for patients with documented coronary artery disease undergoing medical management. These findings suggest that the natural progression of cerebral vascular disease, as opposed to the use of CPB per se, is a major determinant of longitudinal decline in cognition after cardiac surgery.

*Understanding the impact of interventions aimed at reducing brain injury from cardiac surgery on long-term cognition may help assess their overall benefit for patient outcome.*

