In previous work by members of the investigative team, inter-observer point-to-point agreement for analysis of the time-to-peak delay in each area for 12 scans was 83% for calculating the delay to the nearest 0.1 sec and 100% for calculating the delay within 0.2 sec. We will register each image (first registering the corresponding SPGR scans) to a spatial standard, a digital form of the Montreal Neurological Institute atlas, using local registration methods or image warping, in which each voxel is individually displaced. This technique results in better registration to an atlas than do global methods. Registered images are first read by a neuroradiologist and reported in the patient's medical record as part of standard Department of Radiology policy at Northwestern Memorial Hospital. Any subject who enrolls in this study with a history of retained metal in their head and/or eye(s) will have an x-ray of the head done in order to determine if it will be safe to proceed with the MRI. If it is deemed safe for the subject the MRI will be obtained.

Additionally, stored images will be independently analyzed by one of two investigators (TBD) blinded to patient outcomes. The images will be assessed for nonischemic pathology, the presence and location of prior cerebrovascular disease, new acute ischemic lesions, global cerebral edema, and hemorrhages. Acute ischemic lesions will be depicted as a hyperintense signal on the diffusion-weighted images and hypointense signal on the ADC map. ADC can be calculated on a pixel-by-pixel basis. Based on the location, size, and pattern of distribution, the ischemic infarct will be classified into one of four categories: small subcortical infarction (lesion that is  $< 1$  cm in diameter located in the basal ganglia, thalamus, or brainstem); territorial infarction (lesion located in a vascular distribution, usually resulting from large vessel occlusion); watershed infarction (lesion located in the border zone between vascular territories); or multiple emboli (multiple lesions in one or several different vascular territories). The number of acute lesions detected by diffusion-weighted imaging will be counted, and the total infarct volume will be traced and measured volumetrically by a technician using the Image J software. The sum of infarcts and infarct volume will be recorded in addition to the categorization

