of the infarcts as described above. *The primary MRI outcome will be a comparison of the number of diffusion-weighted imaging lesions for patients in the blood pressure Intervention Group with that of the Control Group.*

Secondary analysis will include total infarct volume, location in cortical or subcortical regions, and the ratio of diffusion-weighted imaging lesion size to perfusion-weighted imaging defect size.

MRA will be obtained by contrast-enhanced MRA (CE MRA), using IV contrast at the time of brain MRI. In the event that gadolinium is not administered, MRA of the neck will be carried out with 2D time of flight (TOF) imaging. When gadolinium is administered, neck MRA will be 3D TOF of the neck. MRA of the head will be 3D TOF regardless of use of gadolinium. Measurements of arterial stenosis on MRA will vary depending on the location of the vessel; standard measurements are made by a neuroradiologist, and these will be replicated by one of the investigators (TBD). For extracranial carotid stenosis, the technique is that used in the North American Symptomatic Carotid Endarterectomy Trial (NASCET) (Fig 7).

[figure not shown]
Intracranial arterial stenosis of the most clinically important major vessels (middle cerebral artery, basilar artery, intracranial internal carotid artery) and the extracranial vertebral arteries, will be measured based on the methods used in the Warfarin- Aspirin Symptomatic Intracranial Disease study.

The percent stenosis of a major intracranial artery will be defined as  $[(1 - (\text{Dstenosis}/\text{Dnormal})) \times 100]$ , where

stenosis = the diameter of the artery at the site of the most severe degree of stenosis and normal= the diameter of the proximal normal artery.

For the middle cerebral, intracranial vertebral, and basilar arteries, normal will be defined as the diameter of the widest part of a normal segment of the proximal part of the artery. If this portion of the artery is not normal, then normal will be defined as the diameter of widest part of the distal portion of the artery. When the entire intracranial artery has atherosclerotic narrowing, the most distal part of the normal segment of the artery supplying the vessel will be used for determining normal.

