**Aim 1b: To assess whether targeting MAP to a level above an individual's lower CBF autoregulatory threshold during CPB reduces the frequency of cognitive decline 1 year after surgery compared with the use of standard blood pressure management.** In Aim 1, we will test whether the Intervention and Control groups have the same risk of the primary composite neurologic endpoint of stroke, DWI lesion, or cognitive decline 4 to 6 weeks after surgery (i.e., null hypothesis). This will be done using a two-sided test of proportions at 5% significance level. We will first calculate and report the relative risk (RR) of composite neurologic outcome by comparing the Intervention and Control groups without adjusting for any potential confounders (i.e., the unadjusted RR). In addition, we will construct an adjusted estimate of RR using a generalized linear model (GLM) with Poisson distribution and robust standard errors. The candidate models will include study group as the primary independent variable as well as extra- or intracranial arterial stenosis determined by MRA, patient age, gender, and baseline risk factors that are assumed to be highly predictive of the outcome, such as history of hypertension, diabetes, or prior stroke. To assess potential effect modification by cerebral arterial stenosis, age, gender, hypertension, diabetes, or prior stroke (Aim 1a), we will calculate the unadjusted RR stratified by these variables. We will use a test of homogeneity to compare stratum-specific estimates of RR. Finally, we will use the model developed in Aim 1 to report stratum-specific adjusted estimates of RR by introducing appropriate interaction terms of these variables and study group in the GLM model. We will compute the Z-score for the cognitive tests to normalize the distribution to the control data. The individual Z-scores will be combined into an average score and re-normalized. To assess postoperative change in cognitive function for up to 1 year (Aim 1b), we will use population-average marginal models estimated using generalized estimating equations (GEE) with exchangeable working correlation structure. The model will include assessment time with 2 indicator variables for 1 year and 4 to 6 weeks postoperation and baseline as the reference group as well as Intervention Group, and their interaction to test whether postoperative trajectory of cognitive function differs by group.

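### The SAP permits influential outliers to be dropped from models without limiting this to data errors, so genuine severe injuries could leave the cognitive model (and any lesion-count or volume model) and dilute a real effect

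*Combined protocol and SAP*

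**What the plan says.** The opening paragraph of the Statistical Analysis Plan section states "When conducting modeling, we will determine the influence of the outliers on model fit", and then "If the influence is high, we will consider excluding the outlier/s". It names no influence statistic, threshold, decision-maker or timing, exempts no outcome, and does not restrict exclusion to recording errors. The same paragraph says that the exploratory results will shape the choice of models.

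Three sets of outcomes matter here:

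- **Cognition.** "The cognitive outcome will be assessed as change from baseline in a composite cognitive Z score 4 to 6 weeks after surgery". Timed tests are sign-reversed "so that higher scores represent better performance". Study Statistics (Aim 1b) fits a GEE model with a group-by-time interaction "to test whether postoperative trajectory of cognitive function differs by group".
- **MRI.** Under Magnetic Resonance Imaging, "The number of acute lesions detected by diffusion-weighted imaging will be counted, and the total infarct volume will be traced and measured volumetrically". Lesion number is the primary MRI outcome, and "Secondary analysis will include total infarct volume". No model is named for either.
- **Primary composite.** Study Statistics (Aim 1) uses a two-sided 5% test of proportions on a binary outcome.

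Two other provisions bear on the point. Patient Randomization says that those analysing the data are blinded to group. Missing data rules out imputing outcomes, and its sensitivity analyses concern missing values; none compares results with and without outliers.

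**The concern.** An influence rule is harmless when it leads to the correction of a keying error. Here the extreme values may be the events that the intervention is meant to prevent. A patient with a large perioperative infarct can have a very negative cognitive change, a high lesion count or a large infarct volume, all validly measured. Removing that patient because the value is extreme selects on the outcome after randomisation.

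If the intervention works partly by preventing severe injury, more control than intervention patients are removed and the estimated benefit shrinks. If it does harm, the harm shrinks in the same way. No other provision restores the excluded values or shows the reader what they contributed.

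**Working it through.** **1. Which analyses the sentence reaches.** It applies when models are fitted.

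| Analysis | Outcome | Exposed? |
|---|---|---|
| Aim 1 unadjusted test of proportions | Binary composite | No: not a model, and a severe case is one event however extreme |
| Adjusted relative risks (composite, delirium) | Binary | Within the wording, but there are no extreme outcome values |
| Aim 1b GEE | Continuous Z-score | Yes |
| Lesion number, infarct volume | Count, volume | Only if a model is fitted; none is named |

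**2. Which end is harmful.** For cognition, higher is better, so severe decline is at the low end. Lesion number and infarct volume cannot fall below zero, and zero is the best result, so severe injury is at the high end. As an illustration, take a negative binomial count with mean 2 and dispersion 0.5 (assumed). Its SD is about 3.15, so mean minus 3 SD is 2.0 − 9.45 = −7.45, and no count can be a low outlier. About 2.2% of values are high outliers by a 3 SD rule and 6.3% by the Tukey rule.

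**3. The plan's own cognitive figure.** Inputs from the sample size justification: difference 0.2 SD, within-patient correlation 0.7, two follow-ups, 80% power, 5% error (two-sided assumed).

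- Variance factor for change from baseline: f = (1 + 0.7)/2 + 1 − 2(0.7) = 0.45.
- n = 2 × (1.960 + 0.842)² × 0.45 / 0.2² = 176.6, so 177 per group. This matches the plan.
- SD of change at one follow-up: √(2 × (1 − 0.7)) = √0.6 = 0.775.

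**4. Illustration of the dilution.** There are 177 patients per arm, and change is normal with SD 0.775. A fraction of each arm has an extra drop on the Z scale. The injury rates, drop sizes and cut-offs are assumptions, not document figures. The only anchor is that 5% is the top of the 2%–5% clinical stroke range in Detection of Brain Injury. With everyone kept, the expected difference is (control rate − intervention rate) × drop: 0.02 × 3 = 0.060, or 0.02 × 1.5 = 0.030. Simulated results (3,000 or more replicates):

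| Severe decliners, control vs intervention | Extra drop | Cut | All kept | After exclusion | Lost |
|---|---|---|---|---|---|
| 5% vs 3% | 3 | 3 SD | 0.058 | 0.030 | 48% |
| 5% vs 3% | 3 | 2.5 SD | 0.058 | 0.017 | 71% |
| 5% vs 3% | 1.5 | 3 SD | 0.031 | 0.027 | 13% |
| 5% vs 3% | 1 | 3 SD | 0.021 | 0.020 | 5% |
| 3% vs 5% (harm) | 3 | 3 SD | −0.060 | −0.031 | 48% |
| 5% vs 2% | 3 | 3 SD | 0.089 | 0.037 | 58% |
| 8% vs 3% | 3 | 3 SD | 0.151 | 0.088 | 42% |

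In the first row about 4.0 control and 2.6 intervention patients are removed. I re-ran the 5% vs 3% rows and the harm row, and they agreed within simulation error.

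**5. Effect on inference.** In the first row, the variance is 0.6 + 9 × 0.05 × 0.95 = 1.0275 for control and 0.6 + 9 × 0.03 × 0.97 = 0.8619 for intervention. The standard error is √((1.0275 + 0.8619)/177) = 0.103. The shift of 0.028 is therefore 0.028/0.103 = 0.27 standard errors. If the planned 0.2 SD benefit is added to the same imbalance, the difference is 0.26 with all patients and 0.23 after a 3 SD cut, and power is 71% against 70%. In the 8% vs 3% scenario without that added benefit, power falls from about 27% to 15%. With equal rates (5% vs 5%) and a cut on the pooled data that ignores arm, the false-positive rate stays near 5%.

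**The case against.** The opposing case is substantial, and most of it limits the point rather than removing it.

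- **The primary result is spared.** A reader might infer that the main trial conclusion is at risk. The documents do not support that: the Aim 1 test is an unadjusted comparison of binary outcomes. This stands in full.
- **Analysts are blinded.** A reader might infer that patients could be dropped to favour an arm. The stated blinding limits this. It does not prevent dilution, because a cut that is identical in both arms still removes more patients from the arm with more severe injury.
- **The wording is permissive.** The plan says exclusion will be considered, so it would be wrong to say that it requires deletion. A permission with no bounds is still one that a SAP should not leave open.
- **Scope is partly inferred.** The paragraph begins with data exploration, and the cognitive outcome is described in the next one. No model is named for the MRI outcomes, so the point reaches them only conditionally. The Aim 1b GEE, however, is plainly a model, and nothing exempts it.
- **The size is driven by assumption.** A 3-unit drop is ten times the 0.3 change that the plan counts as decline, and no 2.5 or 3 SD cut appears in the documents. Halving the effect must not be read as the expected loss.
- **The worst cases may be absent anyway.** Experimental Problems lists death, severe stroke and discharge to a care facility as reasons for missed cognitive testing. That may leave fewer extreme Z-scores to exclude, but it does not justify removing those that are measured.

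**Conclusion.** The point holds in a limited form. The SAP permits outcome-dependent exclusion of valid observations from the Aim 1b cognitive model, and from any model that may be fitted to lesion number or infarct volume, with no offsetting analysis. In every imbalanced scenario examined the estimate moved toward zero, for benefit and for harm.

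The amount is uncertain. It ranges from 5% of the difference (1-unit drop, 3 SD cut) to 71% (3-unit drop, 2.5 SD cut) with 5% vs 3% injured, and power is nearly unchanged when the planned 0.2 SD effect is also present. All of these sizes rest on assumed injury rates, drops and cut-offs. The primary test is unaffected. The sentence should be changed, but the trial's main conclusion does not depend on it.

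**What to change.** Replace the exclusion sentence in the Statistical Analysis Plan section with:

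> No valid observation from a randomised patient is excluded from any between-arm comparison because of its influence. Only errors confirmed against source are corrected. Influence is examined in a pre-specified robust or rank-based sensitivity analysis with all patients kept.

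The change should be made before unblinding. It costs one sentence, one extra analysis run and possibly a slightly larger variance in some models. Sample size and trial conduct do not change.

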Under this aim, we will assess whether perioperative TCD findings indicative of arterial stenosis of major cerebral vessels (see **Transcranial Doppler Evaluation**) are predictive of the composite adverse postoperative neurologic outcome. We will test for this possible association by considering - in the multivariable logistic regression model described under Specific Aim 1 - a dummy variable indicative for a positive finding for stenosis preoperatively. Results from this model in conjunction with determination of any potential effect modifications of stenosis on the outcome as described under **Aim 1a** will serve as a valuable tool for assessing the benefits and risks of this CBF-targeted intervention during CPB on patients found to have clinically significant narrowing of the intracranial arteries, as determined by either MRA or TCD examination before surgery.

**Aim 4:** *To assess whether targeting MAP during CPB to a level above an individual's lower CBF autoregulatory threshold during CPB reduces the frequency of postoperative delirium, as assessed with a structured examination, compared with the use of standard blood pressure management.*

In **Aim 4**, we will compare Intervention and Control groups for proportion of patients with delirium. For the analysis, we will include only those patients who have undergone the more extensive delirium assessments as described in this proposal. This same structure assessment for delirium was initiated in year 4 of the prior grant and is consistent with other delirium studies performed by co-investigators (R01 AGO33615). We will estimate the unadjusted (without any other variable in the model) and adjusted RR of delirium by comparing the two study groups. We will adjust for potential confounders using a generalized linear regression model with Poisson distribution and robust standard errors.

**Aim 5:** *To determine whether baseline frailty is independently associated with delirium or functional decline after cardiac surgery.*

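### For the adjusted relative risks in Aims 1 and 4, covariates are left to in-data association and arm imbalance, with no fixed list

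*Combined protocol and SAP*

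**What the plan says.** **Selection rule.** The Statistical Analysis Plan section describes potential confounders as "variables strongly predictive of the outcomes (a priori and in the data) and differentially distributed between the study arms". It continues: "Results of these analyses will be used to refine the analyses and guide model building and selection".

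**Aim 1 (composite neurologic outcome).** Under Study Statistics, the hypothesis test is unadjusted: "This will be done using a two-sided test of proportions at 5% significance level". The unadjusted RR is reported first, and then "we will construct an adjusted estimate of RR using a generalized linear model (GLM) with Poisson distribution and robust standard errors". On covariates: "The candidate models will include study group as the primary independent variable as well as extra- or intracranial arterial stenosis determined by MRA", together with age, gender and "baseline risk factors that are assumed to be highly predictive of the outcome, such as history of hypertension, diabetes, or prior stroke".

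**Aim 4 (delirium).** Unadjusted and adjusted RRs are both estimated, with no order of priority between them. On covariates, the plan says only: "We will adjust for potential confounders using a generalized linear regression model with Poisson distribution and robust standard errors".

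**Related text.** Patient Randomization says that those analysing the data are blinded to group. Perioperative Blood Pressure Monitoring and Recording names postoperative hypotensive episodes in the ICU as a confounder to adjust for.

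**The concern.** In a randomised comparison, a covariate earns its place by being prognostic, whether or not it happens to be imbalanced. A rule that needs both outcome association in the data and imbalance between arms makes the model depend on the realised data. Without cut-offs, it also makes the model depend on the analyst's judgement. Two competent analysts could follow the text and report different adjusted RRs.

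Three features widen the choice:

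- The rule is not limited to pre-randomisation variables. A variable that the intervention changes and that relates to outcome meets both criteria. Adjusting for it could remove part of the treatment effect.
- Under Missing data, the main result is a complete-case analysis when predictor missingness is up to 20%. The choice of covariates can therefore also change which patients are analysed.
- Delirium results by arm have already been seen (33% vs 66% in 37 patients), so the Aim 4 list should not stay open.

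At stake are the reproducibility and error rate of the adjusted estimates for Aims 1 and 4.

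**Working it through.** **1. The plan's own sample size.** Inputs from the sample size section: control rate 0.45, a 40% reduction to 0.27, 80% power, 5% type I error. The two-sided form comes from Study Statistics.

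- Mean rate = 0.36, difference d = 0.18.
- n = [1.960 × √(2 × 0.36 × 0.64) + 0.842 × √(0.45 × 0.55 + 0.27 × 0.73)]² / 0.18² = (1.330 + 0.561)² / 0.0324 ≈ 110.4, so 111 per arm.
- With continuity correction: n/4 × [1 + √(1 + 4/(n × d))]² = 27.6 × (1 + √1.201)² ≈ 121.3, so **122 per arm**, as stated.

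This is a calculation for the unadjusted test. No covariate enters it, so the selection rule cannot change it.

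**2. What the text fixes and leaves open.**

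| Item | Aim 1 | Aim 4 |
|---|---|---|
| Hypothesis test | unadjusted, fixed | priority of unadjusted and adjusted RR not stated |
| Adjusted model form | Poisson, robust errors | Poisson, robust errors |
| Covariates | candidates, open-ended | none named |
| Cut-offs for prediction and imbalance | none | none |
| Selection algorithm | none | none |

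**3. Simulation of the consequence.** There were 4,000 null trials per setting, with 122 patients per arm and an event rate of about 45%. The model is log E(Y) = a + b × arm + c′X, with RR = exp(b) and robust standard errors. Nominal significance is |b/SE| > 1.96. There are six candidate covariates (age and five binary factors), so 2⁶ = 64 possible models, one of which is the unadjusted model.

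Assumptions that are not in the documents:
- odds ratio for each binary factor of 1.5, 2.0 or 3.0;
- age standard normal, with half that log odds ratio per SD;
- binary prevalences of 12% to 75%;
- for the mechanical version of the rule, p < 0.20 for both outcome association and imbalance.

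| Share of null trials with p < 0.05 | OR 1.5 | OR 2.0 | OR 3.0 |
|---|---|---|---|
| Unadjusted | 4.9% | 4.8% | 4.8% |
| Fixed six-covariate model | 5.2% | 5.6% | 5.1% |
| Rule applied mechanically | 4.8% | 4.3% | 3.7% |
| At least one of 64 models, either direction | 8.5% | 10.7% | 13.8% |
| At least one of 64 models, favouring intervention | 4.3% | 5.3% | 6.8% |

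The nominal rate for the last row is 2.5%. Monte Carlo standard errors run from √(0.05 × 0.95/4000) = 0.3 points to √(0.138 × 0.862/4000) = 0.5 points. A rerun reproduced the table. Counting only the 63 adjusted models left the last two rows unchanged, and the five-covariate Aim 1 list proposed under the fix held its error rate as the six-covariate list did.

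**4. Spread of estimates within one trial.** The ratio of the largest to the smallest RR across the 64 models had median 1.06, 1.09 and 1.14 for the three settings. The 90th percentile was 1.11, 1.15 and 1.22.

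**5. Precision.** The SD of log RR was 0.143, 0.137 and 0.132 for the fixed model, against 0.142, 0.138 and 0.133 for the mechanical rule. Precision does not separate the two.

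**The case against.** The strongest reply is that little depends on the adjusted RR. The Aim 1 test is unadjusted and its RR comes first. The analysts are blinded to group. Nothing in the plan describes a search for the smallest p-value, and the nearest mechanical reading of the rule is conservative. All of this stands. It confines the point to the adjusted estimates and makes free choice among models a bound on discretion, not a forecast. Blinding helps, but checking imbalance needs arm codes, and coded arms still show an effect size and a p-value.

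A second reply is that imbalance need not be chance alone. The target is 244 patients with complete endpoint data out of 630 enrolled, and the reasons for a missing MRI arise after surgery. That is fair, but selecting covariates on observed imbalance does not repair such selection. A fixed prognostic list adjusts for the same baseline factors without the discretion.

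A third reply is that the paragraph is general and may serve the observational analyses (time below the autoregulatory threshold, and frailty in Aim 5), where in-data confounder assessment is ordinary. This also stands, so the text should be restricted in scope, not deleted. The reference to study arms still brings the randomised comparisons within it.

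A reader might infer that the trial's primary type I error is inflated, or that the rule inflates error by itself. The documents and the simulation support neither. Nor do the documents say that a favourable adjusted RR may override the unadjusted Aim 1 result.

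**Conclusion.** The concern holds for the adjusted RRs in Aims 1 and 4 only. The plan states a data-dependent selection rule without cut-offs, and no other section closes the choice. The harm comes from discretion. By subtraction from the table, an adjusted RR reaches nominal significance when the unadjusted RR does not in 8.5 − 4.9 ≈ 3.6, 10.7 − 4.8 = 5.9 and 13.8 − 4.8 = 9.0 percent of null trials. These figures rest on assumed covariate strengths and prevalences and on unrestricted choice among six covariates. A smaller or more disciplined search would give less, and a wider pool could give more. For Aim 4 no hierarchy protects the unadjusted RR, so an open list matters more there.

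**What to change.** Before unblinding, state that for Aims 1 and 4 the in-data and imbalance criteria do not apply, and that one adjusted model is fitted per aim, without selection:

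- **Aim 1:** age, sex, hypertension, diabetes, prior stroke.
- **Aim 4:** the same plus baseline MMSE. Add frailty class only if its completeness in the Aim 4 set is confirmed without reference to arm. Structured delirium assessment began in year 4 of the first grant, and the documents do not say whether those early patients had frailty scored.
- **Stenosis on MR angiography:** keep for the Aim 1a effect-modification analysis and a sensitivity model. It is measured at the postoperative scan and is missing for patients without one. If the projections of 180 delirium-assessed patients per arm and 244 with MRI both hold, at least 360 − 244 = 116 of the 360 (32%) would lack it, above the plan's 20% limit for imputation.
- **Post-randomisation variables** such as ICU hypotension: keep out of the main adjusted model.
- **Any other model:** label as exploratory. Report baseline balance descriptively.

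Leave confounder selection for the observational analyses as it is.

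The cost is SAP wording and a few degrees of freedom on covariates that may prove weak. Under the plan's rates, Aim 1 expects 122 × 0.45 + 122 × 0.27 ≈ 88 events, or about 15 for each of six terms (arm plus five covariates). No new data are needed, and the sample size does not change.
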